### **Statistical power and analysis**

**Statistical power.** Differences in weight loss at six mos. between participants randomized to the IP or EUC, and GP or IP are of primary interest. We hypothesize that six month weight loss will average 2 kg, 8 kg, and 12 kg in the EUC, IP, and GP arms, respectively, with a common standard deviation for weight change of 7 kg (34) (35). Statistical power was determined assuming a type 1 error rate of 2.5% for each of our two primary comparisons. Based on these assumptions, randomization of 200 participants with a 2:2:1 allocation; GP (n=80), IP (n=80), EUC (n=40) will provide 98% power to detect significantly greater weight loss in IP versus EUC, and 91% power to detect significantly greater weight loss in GP versus IP. The global F-test for a one-way ANOVA provides greater than 99% power under these assumptions. The primary analysis will be intent-to-treat with imputation of missing data using multiple imputation techniques. However, a completers only analysis, with a 20% loss to follow-up, will still provide 95% power for the IP-EUC, and 83% power for the GP-IP comparisons.

**Analysis plan.** A global one-way ANOVA will be followed with two pairwise t-tests on the two comparisons of interest, IP versus EUC, and GP versus IP. Statistical significance for each pairwise comparisons will be  $p \leq 0.025$ ; however, all other analyses will be conducted at  $p < 0.05$ . These primary analyses will be intent-to-treat utilizing multiple imputation for missing data and to determine corresponding  $p$ -values. In addition to the intent-to-treat analysis, a completers only analysis will be performed, i.e., participants with weight at 6 months. Secondarily, we will compare weight between the three study arms across 24 months using a mixed linear model,

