assuming an autoregressive correlation structure of weight over time, controlling for baseline weight, treatment group and time as covariates. The global comparison across the three arms will be followed by two pairwise comparisons of interest, i.e., IP versus EUC, and GP versus IP. Independent comparisons of change in each chronic disease risk factor, i.e., waist circumference, triglycerides, HDL cholesterol, blood pressure, and fasting glucose at 6, 12, and 18 mos., across the 3 intervention arms will be completed using a mixed linear model, assuming an autoregressive correlations structure. We will also compare Quality of life (SF-36), daily stress associated with eating (Nutrition Hassles Questionnaire), self-efficacy for weight change (WELS), self-efficacy for exercise (EXES), and self-efficacy for overcoming barriers to exercise (BARSE) among the three intervention arms across 24 months using a using a mixed linear model assuming an autoregressive correlation structure both unadjusted and adjusted for covariates. A variety of exploratory analyses, as deemed appropriate by the principal investigator and the project biostatistician, e.g., assessment of the impact of health educator absences and turnover, community environment for healthy eating and PA etc. on weight loss outcomes, will be performed. Analyses will be completed using SAS version 9.4 or higher.

**Missing data.** We will determine if the proportion of participants lost to follow-up differs by intervention arm and/or sex, and compare demographic characteristics between those lost to follow-up and completers. If there are differences across treatment groups, we will examine demographic characteristics, i.e., sex, age, magnitude of weight loss, between completers and those lost to follow-up, to determine if there are significant differences ( $p < 0.05$ ) in those characteristics. If missing data are related to intervention group and/or demographic characteristics, we will use model based multiple imputation; otherwise, traditional multiple imputation will be used.

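### All secondary longitudinal models assume an autoregressive correlation with no alternative, so secondary error bars can be wrong by an amount and in a direction the documents do not settle

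*Combined protocol and SAP*

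**What the plan says.** All of this is in the Analysis plan part of Statistical power and analysis, in the combined protocol and SAP.

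- Weight to 24 months: a mixed linear model "assuming an autoregressive correlation structure of weight over time, controlling for baseline weight, treatment group and time as covariates". It is followed by a global comparison and two pairwise ones (IP-EUC, GP-IP). No treatment-by-time term is listed.
- Change in five risk factors at 6, 12 and 18 months: these comparisons "will be completed using a mixed linear model, assuming an autoregressive correlations structure".
- SF-36, Nutrition Hassles and the self-efficacy scales: a "mixed linear model assuming an autoregressive correlation structure both unadjusted and adjusted for covariates".
- Test level: 0.025 for each primary pairwise test; "however, all other analyses will be conducted at" 0.05.

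The primary 6-month comparison does not use these models. It is a one-way ANOVA and two t-tests with multiple imputation. Study Overview lists weight at 12, 18 and 24 months as a secondary comparison. The only SD given comes from the power statement, "with a common standard deviation for weight change of 7 kg", which refers to 6 months. No later SD and no between-visit correlation is given.

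**The concern.** In its usual form an autoregressive structure makes two assumptions. Every visit has the same variance, and correlation falls as rho, rho squared, rho cubed with the number of visits between measurements. The trial runs through weight loss, maintenance and a no-contact period, and nothing in the documents supports equal spread across them or fast decay of a participant's deviation. For risk factors analysed as change, every visit also shares one baseline reading, which holds the correlation up at long lags.

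These models carry every secondary between-arm comparison of outcomes over time. A wrong covariance misstates the standard errors. With incomplete follow-up it can also shift the estimated means, because missing visits are in effect predicted from the wrong correlations. Four post-baseline visits and 200 participants leave little reason to impose a structure.

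**Working it through.** **1. The plan's own figures.** The documents state no operating characteristic for the mixed models, so the check starts from the primary power statement, to confirm the SD and allocation. The inputs are "six month weight loss will average 2 kg, 8 kg, and 12 kg in the EUC, IP, and GP arms, respectively", SD 7 kg, arms of 80/80/40, and two-sided alpha 0.025.

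- IP-EUC: SE = 7 × √(1/80 + 1/40) = 1.356 kg; 6/1.356 = 4.43; power = Φ(4.43 − 2.24) = 98.6% (98.4% with the t distribution). The plan states 98%.
- GP-IP: SE = 7 × √(2/80) = 1.107 kg; 4/1.107 = 3.61; power = Φ(3.61 − 2.24) = 91.5% (91.0% with t). The plan states 91%.
- With 20% loss, the t calculation gives 95.2% and 83.1%. The plan states 95% and 83%.

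The figures reproduce.

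**2. Visit-specific contrasts, common variance, complete data.** This step assumes arm-by-visit means, which the listed terms do not provide. The model uses approximately the pooled SD, √(mean of SD²), at every visit, so model SE / true SE = pooled SD / SD at that visit. The false-positive rate is 2 × [1 − Φ(1.96 × ratio)]. All SDs after 6 months are assumptions; the falling row also assumes 8 kg at 6 months.

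| SD at 6/12/18/24 months (kg) | Pooled SD | Ratio at 6, 24 months | False positives at 6, 24 months |
|---|---|---|---|
| 7/7/7/7 | 7.00 | 1.00, 1.00 | 5%, 5% |
| 7/7.7/8.3/9 | 8.03 | 1.15, 0.89 | 2.4%, 8.0% |
| 7/8/9/10 | 8.57 | 1.22, 0.86 | 1.6%, 9.3% |
| 8/7.5/7/6.5 | 7.27 | 0.91, 1.12 | 7.5%, 2.8% |

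In kilograms, the true 24-month IP-EUC standard error is 9 × √0.0375 = 1.74 against 1.56 reported in the second row, and 10 × √0.0375 = 1.94 against 1.66 in the third.

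Simulations with drop-out agree. Across separate sets of runs with SD rising to 9-10 kg, false positives were 1-3% at 6 months and 6-11% at 24. In a further set with weight-dependent drop-out, nominal 95% intervals at 24 months covered 90-92% (SD to 9) and 88-90% (SD to 10).

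**3. The visit-averaged contrast implied by the listed terms, constant SD.** Suppose the true correlation is r between every pair of visits. In large samples with complete data, the autoregressive fit takes rho = r, because its likelihood uses only the variances and the lag-1 correlation. With four visits and variance 1:

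- model variance of the average = (1 + r)/(4 − 2r);
- the weights are proportional to 1, 1 − r, 1 − r, 1, so the true variance = r + (1 − r) × [2 + 2(1 − r)²]/(4 − 2r)².

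For r = 0.5 these are 0.500 and 0.639. The SE ratio is √(0.500/0.639) = 0.885, and false positives are 8.3%. For r = 0.7 they are 0.654 and 0.797, ratio 0.906, 7.6%. Simulations with 20-30% missing gave about 6-9% for r between 0.5 and 0.7. With a true autoregressive correlation they gave 4-6%. With rising SD and correlations that decline with lag, this contrast stayed near nominal, at 4-6%.

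**4. Change scores.** With independent, equal-variance visit errors, two changes from one baseline correlate at σ²/(2σ²) = 0.5 at every lag. An autoregressive structure with lag-1 correlation 0.5 forces 0.25 at lag 2.

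**5. Bias under drop-out that depends on the last observed weight change** (24-month contrasts, rising-SD scenarios, 150,000 per arm). Moderate drop-out, with 16-27% lost by arm, gave 0.06-0.11 kg. Strong and unequal drop-out, 20-47% by arm, gave 0.14-0.48 kg. The 0.48 kg comes from an SD rising from 5 to 10 kg; starting from the plan's 7 kg the largest value was 0.35 kg. The empirical standard error at trial size was about 1.5-2.3 kg. An unstructured fit had bias of at most 0.04 kg in large samples and 0.08 kg at 200 participants.

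**The case against.** Autoregressive correlation with visits six months apart is a recognised choice, and the text fixes only a correlation structure. A heterogeneous-variance autoregressive model would satisfy the wording and remove most of the variance problem. That stands as a reason not to call the plan wrong outright. But the plan does not say which form is meant, and heterogeneous variances would leave the decay assumption in place.

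A reader might infer that 6-month error bars will be too wide and 24-month ones too narrow. The documents do not support that as fact. It needs one common variance and an SD that rises with time, and they establish neither. It also concerns visit-specific contrasts, whereas the listed terms give a single average arm difference, which stays near nominal in the rising-SD simulations. The missing treatment-by-visit term is therefore part of the same point.

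A reader might also infer a late bias approaching 1 kg. One set of simulations, with weight-dependent drop-out confined to GP, gave 0.2-0.9 kg for GP-IP, but its unstructured comparator was itself only within about 0.2 kg of zero. The separate calculation in step 5 did not exceed 0.48 kg. Multiple imputation could reduce the bias further if it also feeds these models, which the Missing data paragraph leaves unclear.

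The 0.5 in step 4 depends on equal error variances. With follow-up error SD 1.2 times baseline it is 1/(1 + 1.44) = 0.41. No variances for risk factors or questionnaires are given, so no size can be put on the effect there.

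**Conclusion.** The concern holds as a limited one about secondary results. The plan commits three families of models to an autoregressive correlation without stating the variance assumption or naming an alternative. In the standard form, the consequences under assumed SDs and correlations are:

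- about 6-11% false positives at 24 months and 1-3% at 6 months if the SD of weight grows from 7 to 9-10 kg, reversed if it falls;
- about 6-9% for the visit-averaged contrast if the SD is constant and correlation persists at 0.5-0.7;
- bias of roughly 0.1 kg (moderate) to 0.5 kg (strong) in late contrasts when drop-out depends on earlier weight, minor beside the standard error.

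With constant SD and a correlation that really is autoregressive, there is no error. It would be wrong to extend the point to the main result, because the primary 6-month ANOVA and t-tests do not use these models. The case for changing the plan is that the better method costs almost nothing and needs no guess about variance or decay.

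**What to change.** In the repeated-measures models of the Analysis plan:

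- Use an unstructured covariance with visit as a category, REML and Kenward-Roger degrees of freedom.
- Fix the fallback order for non-convergence: heterogeneous Toeplitz, then heterogeneous autoregressive with empirical standard errors.
- Use only post-baseline visits as the response when baseline is a covariate.
- Add the treatment-by-visit term, so that the weight model delivers the 12, 18 and 24 month comparisons listed in Study Overview.

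The cost is SAP wording and a small change to the SAS code. For four visits the covariance has 4 × 5/2 = 10 parameters instead of 2. There is a small chance of non-convergence, which the fallback order covers.

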Our research team has demonstrated the effectiveness of weight management delivered by university-based health educators via group conference (6 mos. =-10.3%, 18 mos. = - 7.4%) (33, 34), or individual phone (IP) calls (6 mos. = -10.5%) (35) to both urban and rural adults. Weight loss with the group phone (GP) intervention was equivalent to an identical intervention delivered in a traditional on-site group meeting format (34). Telephone delivery eliminates the need for travel to on-site meetings (17). Group phone delivery allows participant interaction which has the potential to increase accountability, social support, and rapport, and has also been associated with reduced drop-out (36) and improved weight loss (37, 38). Group-based interventions may be especially desirable for rural residents who are often socially isolated (39), while the IP approach allows participant anonymity, that some may prefer.

Thus, effective weight management can be achieved when interventions are delivered by university-based health educators using GP or IP approaches. However, the comparative effectiveness of GP and IP interventions, when delivered by rural clinic associated personnel, e.g., nurses, nurse practitioners, physician assistants, or community health professionals trained by our research team, has not been evaluated, and will be the focus of this trial.

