## **Methods and Materials**

### **Study Overview**

Health care providers at five primary care clinics, or community health professionals serving individuals in rural Kansas, will be trained to deliver the GP and IP interventions and an

enhanced version of usual care to compare weight loss (0-6 mos.), weight maintenance (7-18 mos.), and weight change during a 6 mo. period of no contact (19-24 mos.) between interventions. The GP and IP interventions will be identical with the exception of the format (group vs. individual) and duration of contact, i.e., GP (~45 min/session) vs. IP (~15 min/session). Usual care, which is generally limited to brief counseling (5-7 min.) during a routine physician visit and/or referral to a registered dietitian (40), will be enhanced by increased contact with the health care providers and provision of information regarding community assets for increased PA and improved nutrition. We considered using an established weight management intervention such as the Diabetes Prevention Program or Look AHEAD protocols (41-43) as a comparison group. Although efficacious in some settings, the delivery of these interventions is expensive and burdensome for both participants and providers, and are unlikely to be tolerated by rural clinics. Following considerable discussion, we decided to compare our GP and IP interventions to an enhanced version of weight management as currently practiced in rural primary care clinics (40), i.e., enhanced usual care (EUC). Two hundred overweight/obese adults will be randomized in a 2:2:1 allocation to the GP (n=80), IP (n=80), or EUC (n=40) arms. Outcomes will be assessed by the research team at baseline (0 mos.), following weight loss (6 mos.), during weight maintenance (12 and 18 mos.) and after a 6 mo. no-contact period (24 mos.). The primary aim is to compare weight change at 6 mos. between the 3 interventions arms; GP, IP, and EUC, analyzed using intention-to treat principles. Secondarily, we will compare the following across the three interventions groups: 1) weight at 12, 18 and 24 mos. 2) metabolic syndrome risk factors (waist circumference, triglycerides, HDL-cholesterol, blood pressure, fasting glucose) at 6, 12 and 18 mos. Cost, cost effectiveness, and contingent valuation analysis and extensive process evaluation will also be completed. Approval for this study has been obtained from the Human Subjects Committee at the University of Kansas-Lawrence.

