**Group phone intervention: Delivery/session content.** The GP intervention will be delivered to 12-15 participants during a 45 minute call weekly from 0-6 mos. and biweekly from 7-18 mos. using the MaestroConference® software platform (Oakland, CA) that allows group audio conferences to be accessed by phone. Approximately five minutes prior to scheduled meetings, typically late afternoon or early evening, participants will call a toll-free line and enter a unique code number to join the meeting. Participants will be required to remain on the call for the duration of each session to be considered as having attended the session. Call duration for each participant is monitored by the Maestro software. Each meeting will include a check-in question to generate discussion regarding diet and PA, a review of participants self-monitored diet, weight and PA data reported since the previous meeting, a lesson on a weight management topic, and an experiential learning assignment requiring problem solving, or the practice of behavioral strategies, to be completed prior to the next meeting. Sample topics include: energy density (increase volume, not calories), obtaining fruits and vegetables in rural communities, exercising in rural communities, eating/exercising on the go, etc. Several sessions at the end of the weight loss phase (mo. 6) will include discussions regarding complying with a conventional diet, i.e., meal planning, food shopping, meal preparation, portion control, etc. During weight maintenance (7-18 mos.) group sessions will focus on planning and following a meal plan diet with or without incorporation of portion controlled entrées/shakes, and cardinal behaviors for successful weight maintenance such as self-monitoring, regular PA, eating on weekends/vacations, and controlling EI on special occasions and holidays, etc.

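### The secondary 24-month weight model has no arm-by-visit term, so as written it cannot give the arm differences at 12, 18 and 24 months or the no-contact change that the plan sets out to compare

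*Combined protocol and SAP*

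**What the plan says.** The Analysis plan (Statistical power and analysis) introduces the later weight analysis with "Secondarily, we will compare weight between the three study arms across 24 months using a mixed linear model". It assumes an autoregressive correlation and names the terms: "controlling for baseline weight, treatment group and time as covariates". Testing then proceeds as follows: "The global comparison across the three arms will be followed by two pairwise comparisons of interest", namely individual phone (IP) against enhanced usual care (EUC), and group phone (GP) against IP. No interaction is listed and no contrast is tied to a visit.

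The Study Overview asks for more than this. Its first secondary comparison across the three arms is "1) weight at 12, 18 and 24 mos". Its opening description of the trial also includes comparing "weight change during a 6 mo. period of no contact (19-24 mos.) between interventions". No other section gives a separate analysis of weight at 12, 18 or 24 months, or of change over the no-contact period.

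**The concern.** With treatment and time entered only as main effects, each pair of arms is described by a single parameter, so the arm difference is the same at every visit. Coding time as categories or as a trend makes no difference, because either is common to all arms. The between-arm difference in change from month 18 to month 24 is then zero by construction, whatever the data show.

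The follow-up beyond month 6 exists to learn whether an advantage is kept during maintenance and after contact ends. Followed literally, the secondary analysis answers neither question, and a significant pooled effect could be read as a lasting one.

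The design gives some reason to expect differences that change over time. The phone arms have calls "weekly from 0-6 mos. and biweekly from 7-18 mos" and then none, while EUC has four meetings over 18 months. The Introduction reports that an earlier group-phone programme went from 10.3% loss at 6 months to 7.4% at 18 months.

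**Working it through.** **Plan's own figures.** No power or precision is stated for the 24-month model. The stated 6-month power confirms the inputs. With SD 7 kg, losses of 2, 8 and 12 kg, arms of 40, 80 and 80, and two-sided alpha 0.025, t-test power is 98.4% for IP–EUC (stated 98%) and 91.0% for GP–IP (stated 91%). These figures do not rest on the secondary model.

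**Inputs.**
- From the documents: the GP–IP difference at 6 months is 12 − 8 = 4 kg; SD of 6-month change 7 kg; 80 per arm; 5% level for secondary analyses.
- Assumed: the arm differences after month 6; the correlation ρ between adjacent visits; SD 7 kg at later visits; complete data; response at 6, 12, 18 and 24 months with baseline as covariate.

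**What the main-effects model estimates.** Let d be the vector of true arm differences at the four visits and R the AR(1) correlation matrix. The estimate is w′d, with w = R⁻¹1 / (1′R⁻¹1). For four equally spaced visits:
- end visits: w = 1/(4 − 2ρ)
- middle visits: w = (1 − ρ)/(4 − 2ρ)

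At ρ = 0.5 the weights are 0.333, 0.167, 0.167, 0.333. At ρ = 0.9 they are 0.455, 0.045, 0.045, 0.455.

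**Pooled GP–IP estimate (kg) for assumed differences.**

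| True difference at 6/12/18/24 months | ρ = 0.5 | ρ = 0.9 |
|---|---|---|
| 4 / 4 / 4 / 4 | 4.00 | 4.00 |
| 4 / 3 / 2 / 1 | 2.50 | 2.50 |
| 4 / 3 / 2 / 0 | 2.17 | 2.05 |
| 4 / 4 / 4 / 0 | 2.67 | 2.18 |
| 4 / 3.44 / 2.87 / 2.87 | 3.34 | 3.41 |
| 4 / 3.44 / 2.87 / 2 | 3.05 | 3.01 |
| 4 / 3.44 / 2.87 / 1 | 2.72 | 2.56 |
| 4 / 3.44 / 2.87 / 0 | 2.39 | 2.11 |

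The last four rows apply the retained fraction from the Introduction, 7.4/10.3 = 0.72, to both phone arms: 4 × 0.7184 = 2.87 kg at 18 months, with the 12-month value taken midway, (4 + 2.87)/2 = 3.44 kg. The pooled value then exceeds the 24-month difference by about 0.5, 1.0, 1.6–1.7 or 2.1–2.4 kg. In every row, a model with arm-by-visit returns the true values visit by visit.

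**Standard errors.**
- Single visit: 7 × √(1/80 + 1/80) = 1.107 kg.
- Pooled: 1.107 / √(1′R⁻¹1), where 1′R⁻¹1 = (4 − 2ρ)/(1 + ρ). This is 2.00 at ρ = 0.5, giving 0.783 kg, and 1.158 at ρ = 0.9, giving 1.029 kg.

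**How often the pooled effect is significant when the 24-month difference is zero (4/3/2/0).**
- ρ = 0.5: 2.17/0.783 = 2.77, rejection about 79%.
- ρ = 0.9: 2.05/1.029 = 1.99, rejection about 51%.

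A simulation of 200,000 difference vectors per ρ gave 0.792, 0.583 and 0.511 at ρ = 0.5, 0.8 and 0.9. The 24-month contrast from an arm-by-visit model rejected in 0.051, 0.050 and 0.049.

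**Precision cost.** GP–IP 95% half-width at one visit: 1.96 × 1.107 = 2.17 kg. Pooled: 1.96 × 0.783 = 1.53 kg and 1.96 × 1.029 = 2.02 kg. The visit-specific interval is 41% wider at ρ = 0.5 and 8% wider at ρ = 0.9.

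**The case against.** The sentence is a short list of covariates, not a model equation. It does not exclude an interaction, and since the Study Overview names 12, 18 and 24 months, visit-level comparisons may well have been meant. That is fair, and no claim is made about what will actually be fitted. But the terms are enumerated and this one is absent, so two analysts could fit different models and report different secondary results. The clause allowing exploratory analyses does not prespecify a stated comparison.

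The evidence that GP–IP changes over time is thin. Both phone arms share one contact schedule, so the taper bears more on comparisons with EUC. The earlier regain is within a single delivery mode, and regain common to both arms goes into the time effect. If both arms regain the same number of kilograms, the difference stays at 4 kg and there is no distortion. This stands: the kilogram figures show a mechanism and do not forecast a bias.

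The 79% to 51% are not false positives for the pooled hypothesis, because the average difference really is non-zero in that example. The error comes only if the result is read as a 24-month finding. This also stands, though the plan offers no other weight result for 24 months. Finally, the no-contact comparison is in the overview sentence and not in the numbered secondary list; it is still a stated comparison between arms.

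None of this alters the algebra: the listed terms cannot yield the comparisons requested.

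**Conclusion.** The concern holds. As written, the secondary weight model gives one arm difference over all visits. It cannot estimate the differences at 12, 18 and 24 months, and it sets the arm difference in no-contact change to zero. That conclusion needs no assumed effect sizes. The size of any misstatement does: in the GP–IP cases above it runs from zero (constant difference) to 2.67 kg at month 24 (an advantage held to month 18 and then lost, ρ = 0.5), assuming complete data and ρ between 0.5 and 0.9. The 6-month primary analysis, its alpha and the sample size are unaffected. This should be fixed, because the planned analysis does not answer stated secondary questions.

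**What to change.** Specify weights at 6, 12, 18 and 24 months as the response, with baseline weight, arm, categorical visit and arm-by-visit as fixed effects. Prespecify IP–EUC and GP–IP at 12, 18 and 24 months, plus the arm difference in change from month 18 to month 24.

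State the same arm-by-visit form for the risk-factor models. Their fixed effects are not listed, although the Study Overview ties those comparisons to 6, 12 and 18 months.

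A separate and minor suggestion is an unstructured covariance (four visits, 10 parameters) with the autoregressive form as a stated fallback. It does not decide whether visit differences can be estimated.

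The cost is SAP wording and (3 − 1) × (4 − 1) = 6 more fixed-effect parameters, with no new data or participants. The price in precision is the wider visit-specific intervals shown above.

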### **Participant eligibility**

To enhance generalizability of the results, individuals with chronic medical conditions, or common risk factors such as hypertension, tobacco use, hyperlipidemia, diabetes mellitus, etc., who receive clearance from their primary care physician, will be allowed to participate. These individuals are representative of those typically seeking weight management, and that have participated in our previous trials demonstrating the effectiveness of both the GP and IP interventions (34, 48). Medical conditions and medication use may be considered potential confounders; however, randomization should ensure that health status will be similar across study groups. In addition to requiring primary care physical approval, additional inclusion and exclusion criteria (Table 1), and a comprehensive medical management plan have been developed to protect the participants in this trial. Weight loss in high risk participants, i.e., those with chronic conditions or using prescription medications, will be monitored by both the health educators and the study physician. Participants will be asked to report changes in medications

and/or adverse events to the health educators, via toll-free phone call, fax, or email, as they occur.

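### Triglyceride change is modelled with no transformation and no baseline covariate named, which costs precision on one secondary outcome but does not inflate type I error

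*Combined protocol and SAP*

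**What the plan says.** In the Study Overview, triglycerides are among the secondary outcomes: "metabolic syndrome risk factors (waist circumference, triglycerides, HDL-cholesterol, blood pressure, fasting glucose) at 6, 12 and 18 mos".

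The Analysis plan (Statistical power and analysis) treats all five factors alike. The response is change: "Independent comparisons of change in each chronic disease risk factor, i.e., waist circumference, triglycerides, HDL cholesterol, blood pressure, and fasting glucose". The comparisons across the three arms "will be completed using a mixed linear model, assuming an autoregressive correlations structure". Baseline weight is a covariate in the weight model, but no baseline covariate is named for the risk factors. The text names no log, rank or robust method, no residual check and no rule for extreme laboratory values. It does not use the word raw, but untransformed change is its plain reading.

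Participant eligibility opens the trial to "individuals with chronic medical conditions, or common risk factors such as hypertension, tobacco use, hyperlipidemia, diabetes mellitus, etc", subject to physician clearance.

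On the significance level, "however, all other analyses will be conducted at" 0.05. Sidedness is not stated; I take it as two-sided.

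**The concern.** Triglycerides cannot fall below zero, and their spread usually grows with their level. On the raw scale a person with a high value counts far more than one with an ordinary value. As an illustration with made-up values, a fall from 600 to 400 mg/dL is ten times a fall from 120 to 100 (200 against 20). On the log scale the ratio is about 2.2 (ln 1.5 = 0.405 against ln 1.2 = 0.182). Admitting people with hyperlipidemia and diabetes makes a long upper tail plausible, and EUC has only 40 participants.

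An unadjusted change score also leaves in variation that the baseline value would explain. At stake is precision: a real difference in triglycerides could be missed, on an outcome for which the plan has no power calculation.

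**Working it through.** **1. The plan's own power figures.** The plan states: "Statistical power was determined assuming a type 1 error rate of 2.5% for each of our two primary comparisons". Mean losses are assumed as "six month weight loss will average 2 kg, 8 kg, and 12 kg in the EUC, IP, and GP arms", with SD 7 kg. With two-sided alpha 0.025, z = 2.241 and power is approximately Φ(difference/SE − z).
- IP versus EUC: SE = 7·√(1/80 + 1/40) = 1.356; 6/1.356 = 4.43; power 98.6% (98.4% by noncentral t; stated 98%).
- GP versus IP: SE = 7·√(2/80) = 1.107; 4/1.107 = 3.61; power 91.5% (91.0% by t; stated 91%).
- Completers, 20% loss: 95.2% and 83.1% by t (stated 95% and 83%).

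The primary figures reproduce. They concern weight only.

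**2. Assumptions for triglycerides (none is in the documents).** Lognormal values, median 140 mg/dL, log-SD s from 0.3 to 0.6, baseline to follow-up correlation ρ = 0.6 on the log scale, a proportional effect (ratio r), one follow-up visit, 80 IP versus 40 EUC, two-sided 5%.

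**3. Formula check at s = 0.5, r = 0.80.**
- Raw scale: mean M = 140·exp(s²/2) = 158.6; variance V = M²(exp(s²) − 1) = 7148; covariance C = M²(exp(ρs²) − 1) = 4073.
- Variance of change: treated r²V + V − 2rC = 5206; control 2V − 2C = 6150. SE = √(5206/80 + 6150/40) = 14.79. Effect M(1 − r) = 31.7. Effect/SE = 2.14.
- Log scale: SE = s·√(2(1 − ρ))·√(1/80 + 1/40) = 0.0866. Effect −ln 0.80 = 0.223. Effect/SE = 2.58.
- The squared ratio of the two is 1.44, so raw change needs about 1.44 times the participants. The median cancels. For r of 0.80 to 0.85 the factor runs from 1.21 at s = 0.3 to 1.58 at s = 0.6.

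**4. Simulated power, raw change / log change, no baseline covariate** (repeat runs agree within about two points):

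| Reduction | s = 0.3 | s = 0.4 | s = 0.5 | s = 0.6 |
|---|---|---|---|---|
| 10% | 0.47 / 0.51 | 0.29 / 0.33 | 0.19 / 0.23 | 0.15 / 0.18 |
| 15% | 0.81 / 0.87 | 0.56 / 0.64 | 0.37 / 0.46 | 0.25 / 0.33 |
| 20% | 0.97 / 0.99 | 0.82 / 0.90 | 0.59 / 0.73 | 0.43 / 0.55 |

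For GP versus IP (80 versus 80) at s = 0.5 and a 20% reduction: 0.77 / 0.88.

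**5. Adding baseline as a covariate** (IP versus EUC, s = 0.5, 20% reduction): 0.76 raw and 0.82 log, against 0.59 for unadjusted raw change. The covariate alone gains 17 points, the log alone 14, and both together 23.

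**6. Validity and influence.** With no effect, the rejection rate is 0.044 to 0.055 across both scales. At s = 0.4 to 0.6 the largest 5% of changes carry 36 to 46% of the sum of squares on the raw scale, against 27% on the log scale.

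**The case against.** The strongest reply is that nothing in the plan is invalid. Change in mg/dL is a legitimate estimand, the test holds its level, and every triglyceride figure above is assumed. Each part of this stands, and it limits the point in four ways.

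- **False positives.** A reader might infer that a chance imbalance of high values makes spurious effects more likely. The simulations do not support this: type I error is about 5% on both scales.
- **A few people deciding the result.** A reader might say that extreme values dominate the comparison. Under these assumptions the top 5% of changes carry less than half of the variation, and 27% would arise on the log scale anyway. A disproportionate share is as far as the evidence goes. The further criteria in Table 1 may also narrow the tail.
- **The scale as the whole cause.** Much of the shortfall comes from the missing baseline covariate. Once baseline is in both models, the log adds about 6 points (0.76 to 0.82), not 14.
- **Proportional effect.** If only people with a baseline above 150 mg/dL respond (30% reduction, s = 0.5, IP versus EUC), the log scale has no advantage: 0.38 raw against 0.36 log without baseline, and 0.58 against 0.50 with it. Even there, log with baseline (0.50) exceeds the unadjusted raw change of the plan (0.38), because of the covariate.

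The simulation also uses one visit, not the planned three-visit model, so its figures are indicative.

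The plan's allowance for exploratory analyses does not answer the point. Its examples concern weight loss outcomes, and a scale chosen after seeing the data is not pre-specified.

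**Conclusion.** The point holds as an avoidable loss of precision on one of five secondary risk factors. If skewness is moderate and the effect roughly proportional, analysing log change instead of raw change gains between 2 and 14 points of power for IP versus EUC over the range in the table, and 3 to 4 points for a 10% reduction. Using the log together with log baseline raises power from 0.59 to 0.82 at log-SD 0.5 and a 20% reduction. Direction and size rest on the assumed skewness, correlation and proportional effect, since the documents give no triglyceride distribution or target.

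A reader might carry the point over to the trial's main conclusion. The documents do not support that: the primary comparison is 6-month weight, its power figures reproduce, and the sample size does not depend on triglycerides. This is a cheap improvement, not a flaw in validity.

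**What to change.** Add one sentence to the Analysis plan: triglycerides at 6, 12 and 18 months are analysed as log-transformed values in the same mixed model, with log baseline triglycerides as a covariate. Results are reported as ratios of geometric means between arms, with 95% confidence intervals, at each visit. Raw medians and quartiles by arm and visit are given descriptively.

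This needs no extra participants, visits or measurements, and it fixes the scale before the data are seen. The costs are that the result reads as a percent difference instead of mg/dL, and that the log scale brings no advantage if the effect is confined to people with high baseline values.
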